5.1.2. End of Study Definition

The end of the study will occur when the last patient to enter retreatment (per Section 8.1.5) completes the retreatment plus safety follow-up for 5 half-lives (105 days).

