8.1.5. Retreatment

For patients (Group 1 or Group 2) who complete 9 cycles of treatment without disease progression and subsequently experience disease progression during the follow-up period (follow-up visits 1 through 7 only) without any intervening systemic anticancer therapy, resumption of treatment with cemiplimab IV 350 mg Q3W will be allowed per [Table 5](#) (four 12-week cycles). Prior to resumption of cemiplimab treatment, patients must be re-consented (including resigning informed consent) and must repeat all screening activities (with the exception of providing new archived pathology material, research biopsies, or brain MRI), and the investigator must confirm that the patient still meets all eligibility criteria (other than the exclusion regarding prior treatment with anti-PD-1). Such patients will resume cemiplimab 350 mg Q3W monotherapy treatment for 48 weeks (maximum 4 retreatment cycles; 12 weeks per cycle), as per the schedule of events in [Table 5](#). However, PK, ADA, research blood samples, and research tumor biopsies (exploratory “Tumor Biopsies” for Group 2) are not required for these patients during retreatment. In response to AESI like anaphylaxis or hypersensitivity, ADA samples closer to the event may be collected and analyzed, based on the judgement of the medical investigator and/or medical monitor.

After retreatment, patients will be followed quarterly for survival and tumor treatment status, if available, until death. Follow-up status may be determined at clinic visits or via telephone contact with the patient, a family member of the patient, or the physician.

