- **Group 2:** All externally visible BCC lesions should be photographed in a consistent manner at each response assessment as described in [Appendix 5](#). Radiologic imaging (MRI with gadolinium preferred) of anatomic area of externally visible target lesions should be performed at screening and at each response assessment. For each target lesion, the investigator will decide (based on screening imaging) if the radiology (CT or MR) or photo will be the most appropriate method to measure that target lesion, and should use the same modality to measure that target lesion at baseline and at each assessment. If photo is selected to measure a target lesion, imaging (CT or MR) should be obtained to provide supplemental information. In cases in which it is the opinion of the investigator that no significant added information was provided by baseline radiologic imaging of the lesion (beyond the information that was provided by baseline digital medical photography), it is allowed to use digital medical photography only (without radiologic imaging) at

subsequent response assessments of that lesion, at the discretion of the investigator (or vice-versa). If the investigator opts to discontinue cross-sectional radiologic imaging after the baseline assessments and follow the lesion only with digital medical photography (or vice-versa), the reason(s) should be captured in the CRF.

To account for the possibility of unconventional immune responses, immune-related response criteria (irRC) (Nishino 2013) can inform the decision regarding whether to continue treatment for an individual patient if the investigator believes it is in the best clinical interest of the patient, after discussion and approval from the medical monitor. Reasons for any such decision to treat beyond the protocol definitions of progression must be documented in the CRFs. When possible, progression should be confirmed. However, irRC are currently deemed a surrogate endpoint (Postow 2015), and irRC data are not included in the primary endpoint of this study. Any patient who experiences best response (PR or CR) after initial progression (per Appendix 1 or Appendix 2, as appropriate) in the context of continued treatment (according to principles of irRC in after sponsor approval) will not have that best response (partial or complete) counted towards the primary endpoint of this study.

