Although a clear progression of “non-target” lesions only is exceptional, the opinion of the treating physician should prevail in such circumstances, and the progression status should be confirmed at a later time by the review panel (or Principal Investigator).

Evaluation of Overall Response Criteria

The best overall response is the best response recorded from the start of the treatment until disease progression/recurrence (taking as reference for progressive disease the smallest measurements recorded since the treatment started). The patient’s best response assignment will depend on the achievement of both measurement and confirmation criteria. Revised Response Evaluation Criteria in Solid Tumors (RECIST) Version 1.1 ([Eisenhauer 2009](#)) are summarized in the table:

**Response According to Revised Response Evaluation Criteria in Solid Tumors
(Version 1.1)**

Target Lesions	Non-Target Lesions	New Lesions	Overall Response	Best Overall Response when Confirmation is Required^a
CR	CR	No	CR	≥4 weeks confirmation
CR	Non-CR/Non-PD	No	PR	≥4 weeks confirmation
CR	Not evaluated	No	PR	
PR	Non-CR/Non-PD/not evaluated	No	PR	
SD	Non-CR/Non-PD/not evaluated	No	SD	Documented at least once ≥4 weeks from baseline
PD	Any	Yes or No	PD	no prior SD, PR or CR
Any	PD*	Yes or No	PD	
Any	Any	Yes	PD	

CR=complete response; PD=progressive disease; PR=partial response; SD=stable disease.

^a In exceptional circumstances, unequivocal progression in non-target lesions may be accepted as PD.

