An independent central review committee, with access to de-identified digital medical photography results and biopsy results, will provide response assessments as required by the sponsor to address study objectives (Section 5.3.3). Central reviews will be scheduled by the sponsor or designee, but will not be continuous or “real-time.” Clinical management decisions generally will be as per investigator response assessments and local pathology review. In the unlikely event that central review yields major differences with the local response assessment that could have implications for the ongoing management of an active patient on study, the situation will be discussed between the sponsor and the investigator in order to determine patient management.

4) Confirmation of Responses

After any objective response, confirmatory digital photography (and radiologic imaging, if performed as part of the initial response assessment) will be obtained at least 4 weeks following initial documentation of objective response.

For any complete responses observed in digital medical photography of externally visible target lesions, confirmatory biopsies are required to establish status of complete response.

5) Patients in Group 1 with Externally Visible Tumors

Regarding Group 1 (metastatic BCC), these patients will generally be followed by RECIST 1.1 criteria (Appendix 1). It is possible that some patients in Group 1 may also have externally visible lesions that are measurable by digital medical photography. In such circumstances, the externally visible lesions generally will be followed as non-target lesions. The exception to this rule would be a patient with externally visible lesions in whom the only M1 lesions are not measurable by RECIST (eg, a patient with bone-only metastases), in which case the externally visible lesions (lesion size ≥ 10 mm in baseline dimensional perpendicular axes) would be target lesions and followed as per clinical response criteria in this appendix, and the non-measurable metastatic lesions (eg, bone metastases) would be followed as non-target lesions. For any target lesions in Group 1 or Group 2 that are measured by digital medical photography, measurements will be bi-dimensional.

6) Patients in Group 2 with Deeply Invasive Tumors

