1.2.4. Modifications from the Statistical Section in the Final Protocol

Added TTR, DCR, and dDCR as secondary endpoints.

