4.4. Efficacy Variable

4.4.1. Primary Efficacy Variable

The primary objective of the study is to estimate the ORR for mBCC (Group 1) or laBCC (Group 2) according to central review. Objective response rate (ORR) by central review is determined by the proportion of patients with best overall response of CR or PR based on central-reviewed evaluation.

Overall response is determined by RECIST version 1.1 for visceral lesions (Appendix 1 of the protocol), or by modified WHO criteria for skin lesions (Appendix 2 of the protocol), or by the composite response criteria for patients with both visceral and skin lesions (Appendix 2 of the protocol) at each time point at which a response assessment occurs.

Best overall response (BOR) is determined once all the overall response data for the patient are known. The best overall response is the best response recorded during the study:

- Best overall response of CR or PR must be confirmed by consecutive evaluations of overall response of CR or PR at time points at least 4 weeks apart.
- Best overall response of SD must have met the response SD criteria at least once ≥ 39 days (6 weeks – 3 days) after start of study treatment. Best overall response of (early) PD does not require confirmation using the RECIST or the composite response criteria.
- The best overall response for patients who do not have any post-baseline tumor assessment will be not evaluable (NE). Patients with best overall response of NE will be considered as not reaching an objective response of CR or PR.

- Patients with inoperable BCC at baseline who are rendered operable with clear margins will be deemed to have experienced PR.

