4.4.2. Secondary Efficacy Variables

ORR by investigator assessment is determined by the proportion of patients with best overall response of CR or PR based on investigator-assessed evaluation..

Duration of response (DOR) is determined for patients with BOR of CR or PR. DOR is measured from the time measurement criteria are first met for CR/PR (whichever is first recorded) until the first date of recurrent or progressive disease (photographic or radiographic), or death due to any cause.

- Patients who do not have a documented tumor progression or death will be censored at the last evaluable tumor assessment.
- Patients who do not have a documented tumor progression or death before initiation of new anti-cancer therapy will be censored at the last evaluable tumor assessment prior to or on the date of new anti-cancer therapy.
- Patients who do not have any evaluable post-baseline tumor assessment and do not die will be censored on the date of first study treatment.

Progression-free survival (PFS) is measured from the start of treatment until the first date of recurrent or progressive disease (photographic or radiographic), or death due to any cause.

- Patients who do not have a documented tumor progression or death will be censored at the last evaluable tumor assessment.
- Patients who do not have a documented tumor progression or death before initiation of new anti-cancer therapy will be censored at the last evaluable tumor assessment prior to or on the date of new anti-cancer therapy.
- Patients who do not have any evaluable post-baseline tumor assessment and do not die will be censored on the date of first study treatment.

Overall survival (OS) is measured from the start of treatment until death due to any cause. Patients who do not die will be censored at the last date that patient is documented to be alive. As many patients may receive new anti-cancer therapy after disease progression, a sensitivity analysis of OS will be conducted by censoring patients at the first date of a new anti-cancer therapy is taken.

Time to tumor response (TTR) is determined for patients with BOR of CR or PR. TTR is measured from the start of treatment until the time measurement criteria are first met for CR/PR (whichever is first recorded).

For all of the above time-to-event variables, the time to event (day) is the date of event/censor - the date of first study treatment + 1.

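### SAP 4.4.1 sets no stop at progression for best overall response, so read literally it would count post-progression responses that protocol 8.2.2 and Appendix 1 exclude

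*SAP*

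**What the plan says.** - **SAP 4.4.1 (primary variable).** Best overall response is derived after all of a patient's response data are in: "The best overall response is the best response recorded during the study". CR or PR needs two consecutive qualifying evaluations at least 4 weeks apart. Nothing requires either of them to precede PD. Protocol Appendices 1 and 2 are cited for the response at each time point, not for the window.
- **Protocol Appendix 1.** "The best overall response is the best response recorded from the start of the treatment until disease progression/recurrence".
- **Protocol 8.2.2.** A patient "who experiences best response (PR or CR) after initial progression (per Appendix 1 or Appendix 2, as appropriate) in the context of continued treatment" (after sponsor approval) does not have that response counted in the primary endpoint. Both appendices are named, so both groups are covered.
- **Protocol Appendix 2** (the main instrument for Group 2) has no window of its own for best response.
- **Protocol 8.1.5 and 5.1.2.** After nine cycles without PD and then PD in follow-up, "resumption of treatment with cemiplimab IV 350 mg Q3W will be allowed". The study stays open through this phase: "The end of the study will occur when the last patient to enter retreatment (per Section 8.1.5) completes the retreatment plus safety follow-up".
- **SAP 1.2.4** gives the departures from the protocol's statistical section in full as "Added TTR, DCR, and dDCR as secondary endpoints".

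**The concern.** The two documents give different windows for the same variable, and the difference is not declared. SAP 5.8.1, 6.2 and 8 do not restore a stop at PD. An analyst programming from the SAP alone would take the best confirmed response at any time in the study. An analyst programming from the protocol would stop at progression.

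Post-PD response data are foreseen. Section 8.2.2 allows treatment beyond progression because of unconventional immune responses, and 8.1.5 allows 48 weeks of retreatment with scheduled tumour assessments. ORR by central review is the only tested endpoint of what SAP 2.1 calls a pivotal trial, and success depends on an exact lower limit clearing a fixed benchmark. Its numerator should not depend on which document is programmed. The CR rate and the disease control rate use the same best overall response. Durable disease control is less exposed, because its definition also requires absence of progression.

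**Working it through.** **1. One patient under each document.** Take a Group 2 patient with PD at day 64 (end of cycle 1), approved continued treatment, PR at day 127 (end of cycle 2) and confirmation at day 155 (127 + 28).

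- SAP 4.4.1, read literally: a confirmed PR during the study, so a responder.
- Protocol 8.2.2: not a responder for the primary endpoint.
- SAP 4.4.2, PFS: an event at day 64.
- SAP 4.4.2, duration of response: "DOR is measured from the time measurement criteria are first met for CR/PR (whichever is first recorded) until the first date of recurrent" (the sentence goes on to name PD and death as the other end points). The end is day 64 and the start is day 127, and 64 − 127 = −63 days. (The general day-count formula at the end of SAP 4.4.2 runs from first dose, so I use the DOR definition itself.)

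**2. The plan's own figures.** For x responders among n, the Clopper-Pearson lower limit is the 0.025 quantile of Beta(x, n − x + 1). The group succeeds if this exceeds p0.

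- Group 1, n = 50, p0 = 15%: 13/50 gives 0.146 and 14/50 gives 0.162. The cut-off is 14 (28%), and power at 34% is 0.852.
- Group 2, n = 80, p0 = 20%: 23/80 gives 0.192 and 24/80 gives 0.203. The cut-off is 24 (30%), and power at 35% is 0.855.

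Both match the stated thresholds and the stated power of at least 85%.

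**3. Planned enrolment.** Efficacy uses the full analysis set, planned at 53 and 84.

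| Group | One short | Lower limit | At cut-off | Lower limit |
|---|---|---|---|---|
| 1 (p0 = 15%) | 13/53 | 13.8% | 14/53 | 15.3% |
| 2 (p0 = 20%) | 24/84 | 19.2% | 25/84 | 20.3% |

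The adjusted 95.01% interval for Group 1 gives 0.1375 and 0.1525, so the cut-off is the same.

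**4. Illustration.** The documents give no rate of post-PD response. Assume that exactly k = 1, 2 or 3 such patients are added to X ~ Bin(n, p0), where X counts pre-PD responders and their true rate equals the benchmark.

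| k | Group 1: ORR shift k/53 | P(X ≥ 14 − k), n = 53, p = 0.15 | Group 2: ORR shift k/84 | P(X ≥ 25 − k), n = 84, p = 0.20 |
|---|---|---|---|---|
| 0 | 0 | 2.2% | 0 | 2.1% |
| 1 | 1.9 points | 4.7% | 1.2 points | 3.8% |
| 2 | 3.8 points | 9.1% | 2.4 points | 6.4% |
| 3 | 5.7 points | 16.2% | 3.6 points | 10.2% |

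**5. How large the exposed set can be.**

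- A time point with a new lesion remains PD under both appendices, so the PD has to reverse.
- Retreatment can add only a patient who completed nine cycles without PD and never had a confirmed response. Anyone with an earlier one is already a responder.
- Retreatment timing on scheduled scans: week 93 (end of cycle 9) + 8 weeks (follow-up visit 2, the first follow-up scan) = 101; + 12 (first retreatment assessment) = 113; + 4 (confirmation) = 117. The primary cut is about 57 weeks after the last patient's first dose, so only patients enrolled at least 117 − 57 = 60 weeks before the last one can contribute. This allows no time for re-consent and repeat screening, and the enrolment period is not given.
- For RECIST patients, Appendix 1 already bars retreatment responses. For Appendix 2 patients the only exclusion is 8.2.2, whose wording concerns continued treatment and does not clearly reach retreatment.

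**The case against.** The strongest reply is that the protocol still governs. Section 8.2.2 excludes these responses and names both appendices. The SAP rests on the protocol's statistical section and on those appendices, and SAP 1.2.4 lists no change to the window, which may simply mean that none was intended. The DOR definition presupposes that response comes before progression, so a programmer who met a negative duration would stop and ask. The central review charter, which is not among the documents, may end reads at PD.

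Much of this stands. A reader might infer that post-progression responses were, or will be, counted. The documents do not support that: 8.2.2 says the opposite, and the charter may enforce it. A reader might also take retreatment as a substantial leak, or the probabilities in the last table as the trial's true error rate. Neither follows. The retreatment route is nearly empty at the 57-week cut, the values of k are assumed, and any classification question can tip an exact binomial test at its boundary.

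What does not stand is that the SAP needs no change. It does more than stay silent on the window: it states one, and that window differs from the protocol's. Silence in 1.2.4 does not correct it, and an analysis plan should not rely on a programmer noticing an impossible duration.

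**Conclusion.** The rule in SAP 4.4.1 is wrong as written. It conflicts with protocol 8.2.2 in both groups and with Appendix 1 for RECIST patients, and the conflict is undeclared. Applied literally, it would add confirmed post-PD responses to the primary ORR, the CR rate and the disease control rate, and would give those patients a negative DOR. For Appendix 2 patients, exclusion of retreatment responses is not clearly stated anywhere.

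The size is one patient per case: 1.9 points of ORR in Group 1 and 1.2 in Group 2, at planned enrolment. That decides the result only at 13 versus 14 of 53 or 24 versus 25 of 84. The number of such patients is unknown and likely small. The conclusion rests on the texts of the two documents, not on any assumed rate.

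**What to change.** Change SAP 4.4.1 only, for both groups. Proposed text:

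> Best overall response is the best response from start of treatment until first PD, either per Appendix 1 or 2 as assessed by the same reviewer (central for the primary ORR, investigator for investigator-assessed ORR) or as deemed under protocol 7.7.3. The confirming evaluation must also precede that PD. Responses after that PD, including during continued treatment or retreatment, do not count and are listed separately.

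The reviewer must be named because the two reads can differ. Appendix 2 says "Clinical management decisions generally will be as per investigator response assessments and local pathology review", and central review is not in real time, so a patient may stay on treatment after a centrally read PD. The reference to 7.7.3 is needed because palliative radiation is deemed PD there without meeting Appendix 1 or 2, and cemiplimab may be restarted afterwards.

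Protocol 7.3.2.2, on discontinuation at confirmed progression, should stay as it is. It is a treatment rule and has no bearing on the response window.

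The cost is one SAP definition. Sample size, power and thresholds do not change, and no new data are needed: PD dates from both reviews are already required for PFS and DOR. The downside is that the reported ORR may be lower by the number of late responders, who would then appear in a listing.

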Regarding Group 2 (unresectable locally advanced BCC), tumor measurements for these patients will generally be performed with digital medical photography (bi-dimensional measurements). However, some patients in Group 2 may have deeply invasive target lesions in which tumor measurements can better be obtained with cross-sectional imaging (eg, MRI with gadolinium or CT with contrast). For any target lesions in Group 2 or Group 1 that are measured by cross-sectional imaging (eg, MRI with gadolinium or CT with contrast), measurements will be unidimensional according to RECIST 1.1.

Clinical Response Criteria for Externally Visible Tumors (for all patients with locally advanced BCC)

A. Externally Visible Tumor Dimension

The externally visible component of target lesion(s) will be measured using bi-dimensional WHO criteria as the sum of the products (of individual target lesions) in the longest dimension and perpendicular second longest dimension – at each tumor assessment and will be documented using standardized digital photography ([Appendix 5](#)). In the absence of substantial change in lesion geometry, subsequent visit measurements should be performed in the same axes and the investigator should refer to the previous visit's annotated photographs as a starting point to identify axis for measurement when making subsequent assessments.

Clinical response criteria for externally visible tumor(s) require bi-dimensional measurements according to WHO criteria, and are as follows:

- Complete response of externally visible disease (vCR): all target lesion(s) and non-target lesions no longer visible, maintained for at least 4 weeks. Documentation of vCR requires confirmation by biopsies of site(s) of externally visible target lesion(s) with histologic confirmation of no residual malignancy, per central pathology review ([Appendix 4](#)). In the absence of such histologic confirmation, a patient cannot be deemed to have experienced vCR and the best response would be partial response.
- Partial response of externally visible disease (vPR): decrease of 50% (WHO criteria) or greater in the sum the products of perpendicular longest dimensions of target lesion(s), maintained for at least 4 weeks
- Stable externally visible disease (vSD): not meeting criteria for vCR, vPR, or progressive disease

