CR rate is determined by the proportion of patients with best overall response of CR (tumor biopsy confirmation is required for Group 2 patients).

Disease control rate (DCR) is determined by the proportion of patients with BOR of CR, PR, or SD.

Durable disease control rate (dDCR) is defined as the proportion of patients best overall response of CR, PR, or SD without progression for at least 27 weeks (allowing tumor assessment made 1 week earlier than week 27).

Patient-reported quality of life are measured by the EORTC QLQ-C30 (Aronson 1993) and Skindex-16 (Chren 2001) on day 1 of every cycle and at EOT.

- The global health status/QoL, five functional scales (physical, role, cognitive, emotional and social), and three symptom scales (fatigue, pain, nausea and vomiting) and a number of single items assessing additional symptom commonly reported by cancer patients (dyspnoea, loss of appetite, insomnia, constipation and diarrhoea) and perceived financial impact of the disease will be computed using the QLQ-C30 scoring procedures (Fayers 2001).
- The scores for global and three domains of symptoms (4 items), functioning (5 items), and emotions (7 items) will be computed using the Skindex-16 scoring procedures (Chren 2001).
- Change scores are defined as change of summary score of EORTC QLQ-C30 or Skindex-16 from day 1 of first treatment cycle.

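### SAP 4.4.1 confirms CR and PR by one joint rule, so a single RECIST CR next to a PR can count in the CR rate

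*SAP*

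**What the plan says.** SAP 4.4.1 selects the best overall response (BOR) as follows: "The best overall response is the best response recorded during the study". The confirmation rule, with a minimum gap of 4 weeks, then treats the two response categories together: "Best overall response of CR or PR must be confirmed by consecutive evaluations of overall response of CR or PR at time points". No sentence says that a CR needs a second CR, or that a CR with only a PR beside it becomes a PR.

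Two endpoints are built on this BOR. The primary ORR is "the proportion of patients with best overall response of CR or PR based on central-reviewed evaluation". The secondary CR rate is defined in SAP 4.4.2: "CR rate is determined by the proportion of patients with best overall response of CR", with biopsy confirmation added for Group 2 only. SAP 5.8.2 reports the CR rate with a Clopper-Pearson 95% interval.

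The protocol handles CR confirmation in two places.

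- **Appendix 1 (RECIST 1.1):** "The patient’s best response assignment will depend on the achievement of both measurement and confirmation criteria". In its table the CR row has its own entry for confirmation at 4 weeks or more.
- **Appendix 2 (photographed lesions):** visible CR means "all target lesion(s) and non-target lesions no longer visible, maintained for at least 4 weeks", and it also requires negative histology by central pathology. Without that histology the best response is PR.

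SAP 4.4.1 takes its time-point responses from these two appendices.

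**The concern.** A joint rule suits the ORR, because a patient with PR then CR, or CR then PR, is a responder in either case. It does not suit the CR rate, where the split between CR and PR is the whole question. Under the literal wording the pair PR, CR confirms the response, and the best recorded response then labels it CR. A CR seen once would be reported as a confirmed CR.

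The CR rate by central review is a named secondary objective (Protocol 2.2) and endpoint (Protocol 4.2.2). SAP 1.2.4 lists its departures from the protocol's statistical section as the addition of time to response, disease control rate and durable disease control rate. A looser confirmation of CR is not among them. Two programmers working from this text could also derive different CR rates from the same data.

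**Working it through.** **The plan's own figures.** The documents give no target or power for the CR rate. The stated figures concern ORR, and exact binomial calculation reproduces them:

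- Group 1: the smallest count whose Clopper-Pearson lower limit exceeds 15% is 14/50 (28%), with lower limit 0.162; 13/50 gives 0.146. Power at a true ORR of 34% is 85.2%.
- Group 2: the smallest count whose lower limit exceeds 20% is 24/80 (30%), with lower limit 0.203; 23/80 gives 0.192. Power at a true ORR of 35% is 85.5%.

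Nothing below changes these figures.

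**Three readings of the confirmation rule.** Assessments are at least 4 weeks apart. Literal: CR or PR confirms either. Distributive: only CR confirms CR and only PR confirms PR. Split: CR needs a second CR, while PR needs PR or CR followed by PR or CR.

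| Sequence | Literal | Distributive | Split |
|---|---|---|---|
| PR, CR, PD | CR | neither | PR |
| SD, PR, CR | CR | neither | PR |
| PR, CR, PR | CR | neither | PR |
| CR, PR | CR | neither | PR |
| PR, PR, CR, PD | CR | PR | PR |
| PR, CR, CR | CR | CR | CR |
| SD, CR, PD | neither | neither | neither |
| CR, SD | neither | neither | neither |

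The literal and split columns agree on who is a responder in every row, so ORR is the same. They differ on CR in the first five rows. The distributive reading removes the surplus CRs but drops four responders from the ORR.

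**Can the sequence arise?** Appendix 1 asks for a confirmatory scan 4 weeks after objective response is first documented. A patient already in PR has passed that point, and no further scan is clearly required when the PR deepens to CR. The next scheduled assessment is 9 or 12 weeks later, depending on the cycle. A first CR at the last assessment before the data cut, or just before progression, would therefore stand alone.

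**Size per patient.** With planned enrolment as denominator, Group 1 gives 1/53 = 1.9 points. The Group 1 interim analysis uses a subset whose size is not stated. If it were 25 to 50 patients (an assumption), each case would weigh 1/25 = 4.0 to 1/50 = 2.0 points.

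**Illustration.** The documents give no CR count. Assume 5 CRs among 53 Group 1 patients, 2 of them supported only by an adjacent PR:

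- Literal: 5/53 = 9.4% (95% CI 3.1 to 20.7).
- Split: 3/53 = 5.7% (95% CI 1.2 to 15.7).

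**The case against.** The strongest reply is that the SAP sentence is ambiguous and gives no express permission. It can be read distributively, and Appendix 1 never states that the confirming scan must itself show CR. The second part stands: this is a looser and incomplete rule, and a reader who infers an outright contradiction of the protocol goes further than the text allows. The first part does not rescue the wording. On the distributive reading PR, CR, PD has neither a confirmed CR nor a confirmed PR, and the patient is lost from the primary endpoint. No single reading of the sentence serves both endpoints.

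A reader might also infer that the Group 2 CR rate is exposed in the same way, at 1/84 = 1.2 points per patient. The documents do not support that. For photographed lesions in either group, 4-week maintenance and negative central histology are part of the definition of visible CR, and SAP 4.4.1 adopts that definition. An isolated visible CR is not a CR at all. What is left in Group 2 is the radiology-only route in the composite table (clinical component not applicable, RECIST CR), and there SAP 4.4.2 still requires a biopsy.

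Three further points have weight. The frequency is unknown. CR followed by PR should be uncommon under RECIST, because regrowth is judged against the smallest sum on study; from a sum of zero, a 5 mm increase is already progression. And the central review charter, which is not among the documents, may set its own rule for confirming CR.

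**Conclusion.** The point holds as a gap in the SAP's wording for RECIST-derived CR, mainly in Group 1. Taken literally, the joint rule over-counts CR by one patient for each isolated CR next to a PR, or 1.9 points per patient at 53 enrolled. The total effect cannot be estimated from the documents. The conclusion assumes that the central review charter does not already impose CR-by-CR confirmation, and that the 4-week entry on the CR row of Appendix 1 is meant to apply to CR itself.

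It would be wrong to infer any effect on the primary analysis: ORR, its success thresholds and its power are the same under the literal and the split rule. The CR rate is descriptive and untested (Protocol 10.4.3.3, SAP 5.8), so this is a minor point, worth settling before database lock.

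**What to change.** In SAP 4.4.1, replace the joint sentence with a split rule:

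- A RECIST-derived BOR of CR requires a second CR evaluation at least 4 weeks later.
- A BOR of PR requires PR or CR followed by PR or CR at least 4 weeks later.
- A CR supported only by an adjacent PR is classed as PR.
- For lesions assessed by photography, confirmation of CR follows the 4-week maintenance and biopsy requirements of Protocol Appendix 2, and no further CR evaluation is needed.

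The last item matters. Without it, the rule could demand a second overall CR on top of one already maintained and biopsy-proven, and so under-count CR relative to the protocol.

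The cost is a short change of wording and a possibly slightly lower CR rate. ORR is unaffected.
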